## Subject Information

**Target accrual:** We will allocate participating practices in a stepped wedge. There will be four 12-month steps in our design, for a total of 48 months. The first step will be a baseline period in which no intervention is implemented; data collected during this period will provide a within-practice control group for each practice. For the next step, two practices will be randomly selected to receive intervention 1 (Aim 1) and two practices randomly selected to receive intervention 2 (Aim 2). For the third step, the two practices with no intervention will be randomly allocated to 1 or 2; practices initially with intervention 1 will be randomly allocated to 1+2 or 1; and practices initially with intervention 2 will be randomly allocated to 1+2 or 2. For the final step, all practices will receive both interventions. To ensure balance of patient numbers across interventions, we will block randomize at the first step, with the six practices grouped into three pairs according to volume. Physicians, NPs, residents, and patients belong to the individual, geographical separated practices and do not practice or obtain care at more than one practice. The lack of overlap minimizes the risk of contamination.

**Subject population (children, adults, groups):** The units of allocation as mentioned above are the six primary care practices with outcomes being measured at the individual patient-level. For each 12-month-long step, we will measure the HPV vaccination status of the eligible patients empaneled to the providers at that primary care practice.

**Inclusion Criteria:** 1) Empaneled in one of the six participating primary care practices 2) 11 to 12 years of age at the first day of each of the 12-month-long steps 3) Due during that 12-month-long step for at least one dose of the HPV vaccine. (For immunocompetent children (the overwhelming majority), for children less than 15 years of age, the newly revised ACIP recommendations call for two doses at zero- and six-months with the minimum interval being five months between the first and second dose. Some eligible patients may have received two doses too close together for this because of the previous three-dose recommendation was in effect until December 16, 2016, making the ACIP recommendations official. In these cases where the second dose is less than five months after the first, the individual should receive a third dose of HPV vaccine 12 weeks after the second dose and at least 24 weeks after the first dose. Thus, patients who are eligible and due comprise of three groups: those having received no valid HPV vaccine; those having received one valid HPV dose AND it has now been five calendar-months or more; and those having received two valid doses, but Dose 2 was given less than five months after the first. Valid doses include doses given at nine years or older (the minimum age per ACIP) and meet the minimum intervals.

**Exclusion Criteria:** 1) Not empaneled in one of the six participating practices. 2) Empaneled in one of the six participating practices but less than 11 years of age or more than 12 years of age on the first day of each 12-month long step. 3) Not due during that 12-month-long step for a dose of HPV vaccine.

**Waiver for Parental Permission and Child Assent:** We are asking for a waiver of parental permission and child assent appealing to the exceptions permitted under 45 CFR 46 section §46.116. Given that the interventions are allocated at the practice level, the research could not practicably be carried out without the waiver, and the interventions do not exceed minimal risk, the waiver or alteration will not adversely affect the rights and welfare of the subjects, and whenever appropriate, the participants will be provided with additional pertinent information after participation. Parental permission and child assent are impracticable with the overall sample size over the four years of study involve approximately 10,000 children 11 to 12 years of age. It would be impracticable to arrange prospective sessions that would achieve timely informational discussions and provide for documentation of parental permission and adolescent assent for all 10,000 children. Even if we could overcome the logistics, the requirement of consent would compromise scientific validity as the very act of communicating the nature of the interventions (the reminder-recall) would a) serve as an intervention itself altering subjects' behaviors and responses and b) serve to create a selection bias as it would cause parents less likely to vaccinate to opt out of the study leaving those more likely to vaccinate to opt in, biasing the findings. The use of deception is justified as any notification or invitation would serve as its own intervention and confound the impact of the communication of the reminder-recall.

### Statistical Analysis Plan

**Power Statement:** Stepped-wedge cluster randomization trials typically have more statistical power than other cluster randomized designs, because each cluster is able to serve as its own control, accounting directly for the within cluster correlation of outcomes. Because of the complex nature of the design, we estimate statistical power using simulation, which accounted for potential differences in baseline rates across sites. Based on pilot data from a 12-month period, we assumed an average cluster size of 800 children (400 males and 400 females), a baseline probability of requiring any vaccination of 25% (log-odds of -1.1), and a conservative estimate of the standard deviation of the random effect of 0.5, assuming a secular treatment effect. These estimates are conservative. We have sufficient power to detect meaningful patient-centered and provider-level effects in both the sex-stratified and full cohorts. For the interaction between patient-centered and provider-level effects (with the same assumptions described above), based on the simulation, we have at least 80% power to detect an odds ratio (OR) of 1.5 or greater when looking at males and females separately and of 1.34 or greater in the full cohort. To aid in interpretation, an OR of 1.34 means that a significant interaction would be detected if the synergistic effect of the two treatments or interventions is 1.34 times higher than the product of the individual ORs. For example, with ORs of 1.28 for both interventions individually, we can detect a synergistic effect of 2.2. Although our power estimates are conservative, power is somewhat marginal (70% to detect an OR of 1.45) for the synergistic effect in the sex-stratified cohorts; however, we have sufficient power to detect an effect using the combined sample. We conducted several sensitivity analyses adjusting the terms in our model (baseline probability, random effect standard deviation and secular trend) and found small changes in our already conservative power estimates. We used average cluster instead of actual size which was reasonable given our pilot data indicate only a slight imbalance across the clusters. Our average observed total cluster size was 895, with close to 50% male and 50% female; we assumed an average cluster size of 800 (400 for each sex) to allow for decreases in eligible participants overtime as a result of the effect of our interventions.

**Data Analysis Plan:** We will summarize patient characteristics (including sex, age, and race/ethnicity, by intervention status (usual care, parent reminder-recall letters, provider audit-feedback reports, and combination of parent reminder-recall letters, provider audit-feedback reports). All patients will be analyzed on an intention to treat status; this principle will be extended to the practice status, so that delays in implementation of an intervention will not affect the intervention status of patients. We will use generalized linear mixed models to assess the effects of the interventions. All models will be assessed both overall and stratified by sex in recognition of differential rates of HPV vaccination among males and females. Our main model will be a mixed effects logistic regression model which will allow us to test the three primary aims.

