### Research Question and Aims

**Hypothesis:** Our overarching hypothesis is that multilevel interventions for patient, parent, and practice can enhance provider recommendations for HPV vaccination.

**Aims, purpose, or objectives:** We are testing this hypothesis through three phases for which we have developed three protocols. In this third phase, with this protocol, we have three primary aims.

**Aim 1:** Test the hypothesis that, as compared to no intervention, a practice-level intervention utilizing reminder-recalls featuring the availability of non-medication and medication anesthetics, the convenience of nurse-only visits, and the use of persuasive language for early, on-time vaccinations—“Less Pain, Less Fuss, Right Now!”—will improve the odds of a child receiving an HPV vaccine dose by at least 20%.

**Aim 2:** Test the hypothesis that, as compared to no intervention, a provider-level intervention utilizing missed opportunities audit-and-feedback and equipping providers with a strong-recommendation toolkit—“Make It Count!”—will improve the odds of a child receiving an HPV vaccine dose by at least 20%.

**Aim 3:** Test the hypothesis that simultaneous implementation of interventions targeting individual, interpersonal, and organizational factors will have a synergistic effect more than doubling the odds of a child receiving an HPV vaccine dose.

**Background:** Our relevant experience includes our team’s considerable work in vaccine delivery research with particular emphasis on HPV vaccination. This work has focused on parental attitudes toward HPV vaccination, population knowledge and attitudes about HPV vaccination, awareness and knowledge of HPV vaccination among uninsured, low-income populations; factors associated with HPV vaccination initiation and completion, and strategies to address vaccine hesitancy. We have also studied population health interventions that health care organizations can adopt including reminder-recall strategies and others. Our research team partners closely with primary care practice leadership to identify priorities for research to improve the clinical practice and community health. The clinical sites involved in this effort serve as a laboratory for health care delivery research, and our team has significant experience conducting research in these clinics. (See attachments 1, 2, and 3 for letters of support.)

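### The SAP calls single-intervention power sufficient without giving a figure; rebuilt from its own inputs, power is below 80% in each sex at odds ratios 1.20 and 1.28, and in the full cohort at 1.20

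*SAP*

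**What the plan says.** Aims 1 and 2 (Protocol, Research Question and Aims) are primary. Each states that an intervention "will improve the odds of a child receiving an HPV vaccine dose by at least 20" percent, which is an OR of at least 1.20. The comparator is usual care: "as compared to no intervention, a practice-level intervention" is how Aim 1 is framed, and Aim 2 is framed the same way for the provider-level intervention.

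The SAP's Power Statement covers the single effects in one sentence: "We have sufficient power to detect meaningful patient-centered and provider-level effects in both the sex-stratified and full cohorts". It attaches no OR, power or alpha, and alpha appears in neither document. Numbers are given only for the interaction: at least 80% power at OR 1.34 in the full cohort and at OR 1.5 per sex, and, further on, "power is somewhat marginal (70% to detect an OR of 1.45) for the synergistic effect in the sex-stratified cohorts". An OR for a single intervention appears only in an illustration: "with ORs of 1.28 for both interventions individually, we can detect a synergistic effect of 2.2".

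The stated inputs are 800 children per cluster (400 per sex), a random-effect SD of 0.5, a secular effect, and "a baseline probability of requiring any vaccination of 25% (log-odds of -1.1"). The Data Analysis Plan adds: "Our main model will be a mixed effects logistic regression model which will allow us to test the three primary aims". It also says that every model will be run overall and by sex.

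**The concern.** The two single-intervention tests answer two of the three primary aims, yet the plan only asserts their power. The assertion also sits oddly beside the SAP's own standard: it calls 70% per-sex power for the interaction somewhat marginal, but calls per-sex power for the single effects sufficient at an effect size it does not name.

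The Aims are not sex-specific. But all models are run by sex and the Power Statement vouches for both cohorts, so a reader will take a non-significant single effect in boys or girls as adequately tested. If power there is near one half, that reading is wrong.

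**Working it through.** **Inputs from the documents.** Six practices and four steps with the allocation table in the Protocol (Allocation); n = 800 (full) or 400 (per sex); random-intercept SD 0.5; baseline 25%; ORs 1.20 (Aims 1 and 2) and 1.28 (SAP example).

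**Assumptions.** Two-sided 5%; step as a categorical factor; 800 counted per practice per step; the 25% read as the baseline outcome rate. The contrast is not specified, so results are shown with and without the interaction term.

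**Method.** Generalised least squares on the 24 practice-step log-odds. Each cell has variance 1/(n·p·(1−p)):
- n = 800: 1/(800 × 0.25 × 0.75) = 1/150
- n = 400: 1/(400 × 0.25 × 0.75) = 1/75

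Cells of the same practice share covariance 0.5² = 0.25. SEs come from (X′V⁻¹X)⁻¹, and power = Φ(ln OR / SE − 1.96).

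| SE | Full | Per sex |
|---|---|---|
| Interaction | 0.1069 | 0.1510 |
| Single effect, interaction in model | 0.0904 | 0.1276 |
| Single effect, no interaction | 0.0729 | 0.1029 |

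**Step 1: reproduce the SAP's interaction power.**
- Full, OR 1.34: 0.2927/0.1069 − 1.96 = 0.78, power 78%
- Per sex, OR 1.50: 0.4055/0.1510 − 1.96 = 0.73, power 77%
- Per sex, OR 1.45: 0.3716/0.1510 − 1.96 = 0.50, power 69%

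A binomial simulation (4,000 replicates, no trend) gives 80%, 79% and 71%, against the stated 80%, 80% and 70%. A second simulation with true single effects of 1.20 or 1.28 gives 81–82%, 79–80% and about 72%. Other readings do not match. Linear time or no time term gives 98–99% at 1.34 (full) and 95–97% at 1.45 (per sex). Reading 800 as the total over four steps gives at most about 56%.

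**Step 2: single-effect power in that setting.** Worked at the lower end:
- Full, 1.20, with interaction: 0.1823/0.0904 − 1.96 = 0.06, 52%; without: 0.1823/0.0729 − 1.96 = 0.54, 71%
- Per sex, 1.28, with interaction: 0.2469/0.1276 − 1.96 = −0.03, 49%; without: 0.2469/0.1029 − 1.96 = 0.44, 67%

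Ranges over the analytic and simulated runs, including a true trend of 0.1 log-odds per step:

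| | With interaction | Without |
|---|---|---|
| Full, OR 1.20 | 52–56% | 71–75% |
| Full, OR 1.28 | 78–81% | 92–95% |
| Per sex, OR 1.20 | 29–33% | 43–46% |
| Per sex, OR 1.28 | 49–54% | 67–73% |

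The OR detectable at 80% power, exp(2.80 × SE), is 1.28–1.29 with and 1.22–1.23 without the interaction (full), and 1.41–1.43 and 1.31–1.33 (per sex). The lower end of each range allows for the rise in event rate under the interventions.

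**Step 3: back-calculate from the SAP's own interaction power, without using the 25%.** Treat 'at least 80%' as 80%. The implied interaction SE is 0.2927/(1.960 + 0.842) = 0.1045 (full). Per sex it is 0.4055/2.802 = 0.1447 or 0.3716/(1.960 + 0.524) = 0.1496. The design fixes the ratio of single-effect to interaction SE at 0.846 with and 0.682 without the interaction. Implied power, with / without:
- Full: 54% / 73% at 1.20; 80% / 93% at 1.28
- Per sex: 50–52% / 68–71% at 1.28

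**Step 4: look for a setting that rescues the claim** (with / without the interaction).
- Observed cluster size 895: full at 1.20, 57–59% / 75–79%; per sex at 1.28, 53–56% / 72–76%.
- Baseline 50%, the most favourable rate: per sex at 1.28, 61% / 79%; full at 1.20, 64% / 82%. Only the last figure passes 80%, and Step 3, which does not use the rate, gives 73% there.
- Linear time: full at 1.20, 61–64% / 71–74%; per sex at 1.28, 57–61% / 67–72%.
- No time term: full at 1.20, 91–92% / 99%; per sex at 1.28, 88–90% / 99%. But the SAP describes "adjusting the terms in our model (baseline probability, random effect standard deviation and secular trend"), and this setting gives 95–97% where the SAP states 70%.
- One-sided 5%, no interaction: full at 1.20, 80–83%; per sex at 1.28, 78–81%. But interaction power at 1.45 then becomes 79–83%, not 70%. If the SAP's interaction power is held and Step 3 is redone one-sided, per-sex power at 1.28 is 52–56% / 68–72%.

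**The case against.** The strongest reply is that no stated figure is wrong. The sentence carries no number and leaves 'meaningful' undefined, and the figures the SAP does give can be reproduced. The SAP never says that the trial is powered at 1.20. Its interaction text accepts per-sex ORs of 1.45–1.5, so per-sex detectable ORs of 1.31–1.43 might count as meaningful too. That is a possible reading, but neither document names any single-effect OR other than 1.20 and 1.28, so the claim has no stated effect size at which it holds per sex.

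The second reply concerns the contrast. The SAP does not say how the interventions are coded. An effect-coded factorial model can contain the interaction and still have the smaller SEs (0.0729 and 0.1029). With single ORs of 1.28 and an interaction of 1.5, the averaged effect would have about 99% power per sex. This stands in part: the choice moves per-sex power at 1.28 by about 18–20 points. But that averaged effect blends the single and synergistic effects, while Aims 1 and 2 compare each intervention with no intervention. If there is no true interaction, the smaller SEs still leave per-sex power below 80% at both ORs.

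The match to the SAP's interaction power is also within a few points rather than exact. That does not reverse any per-sex result. Finally, the full-cohort claim is close to confirmed at 1.28, and this is accepted.

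**Conclusion.** The concern holds. In the setting that comes close to the SAP's interaction power, the sex-stratified cohorts do not reach 80% power for a single intervention at either OR the documents name. At 1.28, power is about half with the interaction in the model. Without it, power is about the 70% that the SAP itself labels marginal. A true OR of 1.28 would be missed in a given sex 46–51% of the time with the interaction and 27–33% without. In the full cohort the claim is defensible at about 1.28, but a true OR of 1.20 would be missed 44–48% / 25–29% of the time.

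Confidence is moderate. Alpha, the form of time, the contrast and the reading of the 25% are assumptions, and the sponsor's simulation is not shown. The comparator in Aims 1 and 2 and the single main model for all three aims favour the with-interaction figures, but the SAP does not settle this. The per-sex conclusion survives either contrast and any baseline rate under two-sided 5% with categorical step effects. The settings that lift per-sex power at 1.28 to about 80% or more, no time term or a one-sided test without the interaction, conflict with the SAP's stated 70%.

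**What to change.** Replace the sentence with single-effect power from the sponsor's own simulation at OR 1.20 and 1.28, in the full cohort and per sex, together with the OR detectable at 80% power. State alpha and sidedness, the time terms, whether the interaction is in the model, and which contrast tests Aims 1 and 2.

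Unless that simulation shows otherwise, drop the claim of sufficient power for the sex-stratified cohorts. In the full cohort, limit it to effects of about OR 1.28, or about 1.22–1.23 if the single effects are tested without the interaction. The figures above show why the sentence needs support; they do not replace the sponsor's simulation.

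The cost is SAP wording drawn from a simulation the sponsor says it has run, plus a less favourable stated power for the single effects, mainly per sex. No extra patients are needed, and design, sample size and planned models stay as they are.

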### Endpoints

Our outcome variables are the rates of HPV-vaccine receipt for empaneled eligible males and females, measured at the end of the last day of each 12-month step. Furthermore, eligible individuals must be due for a dose of an HPV vaccine at the start of the 12-month-long step. They could be due for the first, second, or third dose. Eligibility for a dose depends on previously received valid doses received before the beginning of the 12-month-long step. Eligibility also depends upon the amount of time that passed between the last received valid dose and the start of the 12-month-long step. Valid doses include doses given at nine years or older (the minimum age permitted by the ACIP) and meet the minimum intervals. If the individual has received no valid doses previously at age 11 or 12, then the individual is eligible for a first dose. If the individual has previously received one valid dose, and at least 5 months has passed since that dose before the start of the 12-month-long step, then the individual is eligible for a second dose. If the individual has previously received two valid doses but the second dose was given less than 5 months from the first and at least 12 weeks have passed since the second dose and 24 weeks since the first dose, both before the start of the 12-month-long step, then the individual is eligible for a third dose.
